## Follow-up (Days 2, 3, 4,5,6, 7,8,9, 10, and 28)

The following will be performed, updated and recorded in the CRF.

- Time when diagnostic tests were made available to the nursing/medical staff,
- Treatment, specifically the relationship between the timing/availability of diagnostic tests and changes in antimicrobial therapy. The nature of treatment given to all patients within 10 days of admission will be documented,
- Isolation, specifically the relationship between the timing/availability of diagnostic tests and changes in isolation status. The isolation status of all patients throughout the first 7 days of admission will be carefully documented,
- Admission to ITU and ventilatory support (within 28 days of hospitalisation),
- Pyrexia the timepoint when the patient first became apyrexial  $(\leq 37.2^{\circ}C)$ , and remained so for >24 hours (during days 1-10)
- Oxygen requirement the timepoint when supplemental oxygen was no longer required, and was not given for >24 hours (during days 1-10)
- Diagnostic studies (within 28 days of hospitalisation)

•	Duration	of hos	spitalis	sation
---	----------	--------	----------	--------

- Deaths (within 28 days of hospitalisation)
- EuroQol (Days 7 and 28)
- Discharge diagnosis
- Convalescent serum sample (Day 10 90)

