## TRIAL PLAN AND SCHEDULE OF ASSESSMENT

Note: Patients WILL NOT be re-recruited if readmission occurs during the 28-day follow-up

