The costs of performing rapid molecular and near patient diagnostic tests for influenza, RSV and S. pneumoniae infections, differ significantly from the cost of traditional laboratory culture.

6. Assess cost-savings associated with earlier use of narrow-spectrum antimicrobial therapy (or avoidance or discontinuation of antibiotics) in patients whose influenza, RSV and *S. pneumoniae* infections are diagnosed more rapidly by rapid molecular and near patient diagnostic tests, in comparison to traditional laboratory culture.

The earlier use of narrow-spectrum antimicrobial therapy (or avoidance or discontinuation of antibiotics) in patients whose influenza, RSV and S. pneumoniae infections are diagnosed more rapidly by rapid molecular and near patient diagnostic tests results in significant cost-savings, in comparison to traditional laboratory culture.

7. Compare the outcome of patients whose influenza, RSV, and *S. pneumoniae* is diagnosed more rapidly by rapid molecular and near patient diagnostic tests, compared to those who are diagnosed by traditional laboratory culture.

A streamlining of antimicrobial prescribing that may arise from more rapid diagnosis of influenza, RSV and S. pneumoniae infections by rapid molecular and near patient diagnostic tests does not adversely affect patient outcome.

8. Assess the impact that rapid molecular and near patient diagnostic tests have on the costs associated with an inpatient stay and on costs post-discharge up to a maximum of 28 days after admission.

Any increase in costs incurred by rapid molecular and near patient diagnostic tests, in comparison to traditional laboratory culture, is more than offset by savings that arise from either rational antimicrobial prescribing or earlier discharge from the hospital.

9. To assess the impact that rapid molecular and near patient diagnostic tests have on quality-of-life, as measured by the EuroQol (Appendix I), and to use this information to estimate the quality adjusted life years (QALYs) generated during the 28 days after admission.

Rapid molecular and near patient diagnostic tests result in an improvement in quality-of-life, as measured by the EuroQol, which arises from streamlining of antibiotics and earlier discharge into the community.

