*Duration of hospitalisation* The duration of hospitalisation, until discharge or death, will be obtained from the hospital activity analysis (i.e., computerised records). It will not form part of the routine monitoring of patients by the study nurse.

*Discharge diagnosis* The patient's discharge diagnosis will be obtained from the hospital activity analysis (i.e., computerised records). It will not form part of the routine monitoring of patients by the study nurse.

*Resource use after discharge* General practitioner consultations, hospital follow-up and other resource implications (e.g., prescriptions) for the period from discharge until Day 28 will be captured by a postal questionnaire (Appendix I). Patients will receive a reminder telephone call on Day 28 to return the questionnaire by post.

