#### 5 STUDY POPULATION

#### 5.1 Study setting

This study will be done in three hospitals (Leicester Royal Infirmary, Glenfield Hospital, and Leicester General Hospital) that provide acute medical care for the University Hospitals of Leicester (UHL) Trust, Principally in the Medical Assessment Units. The UHL Trust serves a population of approximately 1 million subjects of all ages. The University Hospitals of Leicester NHS Trust is the only facility within the county of Leicestershire providing inpatient emergency medical care to the inhabitants of Leicestershire (population ~ 1 million). The laboratory tests will be carried out in the Molecular Diagnostic Laboratory, and Public Health Laboratory, Leicester Royal Infirmary. The study will carried out during the 36-month period August 1 2005- July 31 2008. Patient enrolment will occur during: September 1 2005 to June 30 2006; September 1 2006 to June 30 2007; & September 1 2007 to June 30 2008.

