#### 6.2.4 Diagnostic tests, procedures, and other resource implications (Days 2, 3, 4, 7, 10, and 28)

The following resources used by study participants will be recorded in the CRF:

- 1. **Diagnostic tests/procedures** The number and type of all investigations and procedures that were carried out by the medical team, up to a maximum of 28 days (up to midnight of day 28) following admission, will be recorded in the CRF. This information will be obtained following discharge from hospital or death, by reference to APEX and examination of the case-notes and X-rays.
- Additional treatment/support The participant may require additional treatment or support, for example from a medical or nurse specialist, physiotherapist, nutritionists, occupational therapy, etc. This will be identified by reference to the medical records on discharge and recorded in the CRF.
- 3. **Discharge medication** The name, dose, frequency, and duration of any newly prescribed discharge medication (i.e., additional to regular prescriptions) will be recorded in the CRF for discharges occurring within 28 days of admission, by reference to the discharge letter.

- 4. **Hospital follow-up** The nature of further investigations (e.g., Chest-X-ray) and hospital follow-up visits that occur within 28 days of admission will be recorded in the CRF. This information will be captured by a Questionnaire (Appendix I, see Pages 60 and 65).
- 5. General practitioner consultations (Day 28) The number of occasions that patients were seen by their GP or deputising doctor after discharge (up to 28 days following admission), and whether it occurred in the surgery, another medical centre, or in the patient's home will be recorded in the CRF. This information together with the nature of any treatment received will be captured by a Questionnaire (Appendix I, see Pages 60 and 65).

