#### HOSPIAL HEADED NOTEPAPER

#### Day 28 postal questionnaire

# A RANDOMISED CONTROLLED TRIAL TO EVALUATE IMPACT OF DIAGNOSTIC TESTING FOR INFLUENZA, RESPIRATORY SYNCYTIAL VIRUS AND STREPTOCOCCUS PNEUMONIAE INFECTION ON THE MANAGEMENT OF ACUTE ADMISSIONS IN THE ELDERLY AND HIGH-RISK ADULTS.

Name	Study Number
Admission date//	Discharge date//
Date of 28 days from admission date	//

During your recent stay in hospital you kindly agreed to take part in the above study. As part of this research we would like to ask you a few questions about any health care you have received since you were discharged from hospital

We would also like to ask you a few simple questions about your health today.

**Question 1.** Firstly, we would like to ask you if any of the following health care professionals have visited you in your own home since you were discharged from hospital? For each type of person, please tick the box if you saw this health care professional and tell us how many times you saw this person. Remember, here we are only interested in health care you have received in your own home.

1	GP	How many times?
$\square_2$	District nurse	How many times?
3	Practice nurse	How many times?
4	Other nurse	How many times?
5	Home care worker/ home help	How many times?
6	Other person (please specify)	How many times?
7	Other person (please specify)	How many times?
8	Other person (please specify)	How many times?

**Question 2.** We would now like you to think of any health care professionals that you might have seen outside your own home since you were discharged from hospital. For each type of person, please tick the box if you saw this health care professional and tell us how many times you saw this person. Remember, here we are only interested in visits you have made to receive healthcare outside your home.

1	Hospital doctor in outpatients department	How many times?
$\square_2$	GP	How many times?
3	Practice nurse	How many times?
4	Other nurse	How many times?
5	A&E department	How many times?
6	Other (please specify)	How many times?
7	Other (please specify)	How many times?
8	Other (please specify)	How many times?

**Question 3.** Since your discharge from hospital have you had any extra medicines prescribed for you?

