(Please do not include any medicines you were prescribed in hospital, or any medicines that you regularly received before your stay in hospital. We are only interested in extra medicines that have been prescribed since you were discharged from hospital.)

 $\begin{array}{c|c} YES & \square_1 \\ NO & \square_2 \end{array}$ 

If YES: How many new medicines have you been prescribed? \_\_\_\_\_\_ For each new medicine could you tell us the name of this medicine and how long (in days) the prescription was for? Please place your answers in the boxes below

	Name of Medicine	How long for?
1		
2		
3		
4		
5		

**Question 4.** Since your discharge from hospital have you bought any non-prescription medicines 'over-the-counter'; for example, in chemists, supermarkets, or other shops. Please also include any medicines that were bought for you by other people. Again, we are interested only in the period since your discharge from hospital.

If yes, how many 'over-the-counter' medicines have you purchased or had purchased for you since you were discharged from hospital?

For each medicine could you tell us the name of this medicine, the number of items (i.e. packets, bottles, or tubes) and the approximate packet size. Please place your answers in the boxes below

	Name of Medicine	Number of items	Approximate packet size
1			
2			
3			
4			
5			

**Question 5.** We would now like you to think about your health today. By placing a tick in one box in each group below, please indicate which statements best describe your own health state today.

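### The 28-day care cost has no stated source for readmission bed-days, so the cost comparison can favour the rapid tests if earlier discharge leads to more returns

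*Protocol*

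**What the plan says.** **Aim.** Section 2.1, objective 8, covers inpatient cost and post-discharge cost within 28 days of admission. Its hypothesis is that any extra test cost is outweighed by "savings that arise from either rational antimicrobial prescribing or earlier discharge from the hospital". Cost per QALY is one of two main economic outcomes (section 7.5.2).

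**Bed-days.** The synopsis (Financial, item 7) builds inpatient cost from length of stay and a daily hotel cost, then adds further care. Sections 4.1 and 6.2.10 take length of stay from the hospital activity analysis, as one stay that ends when the patient is discharged or dies.

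**After discharge.** Section 4.1 says that resource use "for the period from discharge until Day 28 will be captured by a postal questionnaire". The synopsis and section 7.5.2 also allow a telephone interview. Section 6.2.4, item 4, says that further investigations and "hospital follow-up visits that occur within 28 days of admission will be recorded in the CRF", again by questionnaire.

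**The Day 28 forms (Appendix I).** The postal and telephone versions have the same content: home visits, care outside the home, newly prescribed medicines and over-the-counter medicines. The hospital items under care outside the home are "Hospital doctor in outpatients department" and A&E attendance. Three free-text lines follow.

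**Readmission.** It appears as a bar to a second enrolment, for example in the note to the trial plan: "Patients WILL NOT be re-recruited if readmission occurs during the 28-day follow-up".

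**The concern.** A 28-day cost should count every bed-day in the 28 days, whichever stay it belongs to. Here the first stay has a record-based count of days and any later stay has none.

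The gap lies where the cost hypothesis is most exposed. Shorter stays are one of its two routes to savings, and readmission is the direct counter-event to a shorter stay. It also bears on hypothesis 7, that streamlined prescribing does no harm. A bed-day saved at discharge would be credited in full, and a bed-day used on return would not be charged. Any such error carries through to cost per QALY.

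**Working it through.** **1. Is there any source of readmission bed-days?** Each source of data after discharge was read in turn.

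| Source | What it gives | Readmission bed-days? |
|---|---|---|
| Hospital activity analysis (4.1, 6.2.10) | Duration of one stay, discharge diagnosis | No |
| Pathology system, case-notes, X-rays (6.2.4, item 1) | Investigations and procedures to Day 28 | No |
| Discharge letter (6.2.4, item 3) | Discharge medicines | No |
| Day 28 postal and telephone forms | Contacts with professionals, A&E, medicines | No; A&E or free-text lines may reveal the event, without its length |
| Hospital information systems (7.6, Cost data) | Time of discharge, to extrapolate costs of patients still in hospital at Day 28 | No |

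**2. What does the omission do to the comparison?** For each arm let S be mean bed-days in the first stay, p the proportion readmitted, and L the mean readmission bed-days, per readmitted patient, that fall within 28 days of the first admission.

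- Full bed-days to Day 28: S + pL
- Bed-days counted under the plan: S
- Part of the rapid-minus-control difference that is missed, with the same L in both arms: (p_rapid − p_control) × L

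If p is equal in the two arms, the missed part of the difference is zero and only the totals fall. If p is higher in a rapid arm, that arm looks cheaper than it is. If p is lower, it looks dearer.

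**3. The plan's own yardstick.** Section 7.4 uses a 1-day difference in mean stay, SD 6, 2752 patients, 20% dropout and three groups, and states power over 80%. Equal allocation and two-sided tests are assumed here.

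- Patients per arm: 2752 × 0.8 / 3 = 733.9
- Standard error: 6 × √(2/733.9) = 0.313, so 1/0.313 = 3.19
- Power at alpha 0.05: 89.1%
- Power at 0.05/2 (two comparisons with control): 82.9%
- Power at 0.05/3 (all pairs): 78.8%

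The stated figure is reproduced with two comparisons against control. It is not in dispute; the 1-day difference serves as the scale below.

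**4. Size, under assumptions.** The protocol gives no readmission rate, readmission stay or unit cost. Bed-days missed per patient equal extra readmissions × L; the break-even excess for a 1-day saving is 1/L.

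| L (days) | 2 points extra | 5 points extra | 10 points extra | Excess that cancels 1 day |
|---|---|---|---|---|
| 4 | 0.08 | 0.20 | 0.40 | 25 points |
| 8 | 0.16 | 0.40 | 0.80 | 12.5 points |
| 12 | 0.24 | 0.60 | 1.20 | 8.3 points |

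At L = 8, an excess of 3 points gives 0.03 × 8 = 0.24 bed-days and 5 points gives 0.05 × 8 = 0.40. These are 24% and 40% of a 1-day saving.

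**5. A separate inconsistency.** The synopsis follow-up list has "Admission to ITU and ventilatory support (within 28 days of hospitalisation". Section 4.1, section 6.2.7 and endpoints 2(d) and 2(e) in the synopsis and section 7.5.1 use the first 10 days. Section 6.2.7 records total ICU duration, but on its wording an ICU admission after Day 10 is not captured, although care is costed to Day 28.

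**The case against.** The strongest reply is that the information is not lost. Section 5.1 says that the Trust "is the only facility within the county of Leicestershire providing inpatient emergency medical care", and its activity records already supply length of stay, so readmissions could be extracted later. This stands as a reason why the repair is easy. It does not close the gap, because the protocol names what is taken from those records and readmissions are not included. An analysis plan cannot cost bed-days that no form or extract obtains.

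Several stronger readings are tempting, and the documents do not support them:

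- **That everything after discharge rests on the questionnaire.** Investigations and procedures to Day 28 come from laboratory records and case-notes, so tests done at a readmission within the Trust are arguably covered.
- **That readmissions leave no trace.** The A&E item and the free-text lines may show one. They ask about contacts and counts, not nights.
- **That this is the largest cost of early discharge.** No unit costs are given, so it cannot be shown.
- **That the rapid arms will look falsely cheap.** This needs both earlier discharge and more readmissions in those arms.
- **That a safety signal is lost.** Deaths to Day 28 are reported with study group, with a route to the data monitoring committee (section 10.4), and EuroQol is collected on Day 28. One measure of hospital use is missing.

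The instruction in Question 3, "Please do not include any medicines you were prescribed in hospital", is also weak evidence of a defect. Inpatient and discharge medicines are already recorded from prescription charts and discharge letters, so it avoids double counting.

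**Conclusion.** The point holds in this form: the 28-day care cost counts bed-days for the first stay, and no stated source yields bed-days for a readmission. Total costs are understated in every arm that has readmissions. The comparison between arms, and cost per QALY with it, is biased only if readmission differs between arms; the bias is towards the rapid tests if they discharge earlier and have more returns.

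The size is unknown. On an assumed 8-day readmission, an excess of 3 to 5 points would hide roughly a quarter to two-fifths of a 1-day saving, and reversal would need more than 12.5 points. Material distortion is plausible; reversal would require a large excess. No sample-size figure changes. The 10-day versus 28-day ICU window is a separate inconsistency and adds no weight to this conclusion.

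**What to change.** 1. In sections 6.2.4 and 6.2.10, state that all readmissions within 28 days of the first admission (dates, bed-days, ward or ICU) are extracted from the hospital activity analysis for all three groups.
2. Add these bed-days to the 28-day care cost. Report total bed-days to Day 28 and the proportion readmitted beside length of the first stay.
3. Add one line to both Day 28 forms asking about overnight hospital stays since discharge and the number of nights, to catch admissions outside the county.
4. Separately, reconcile the ICU and ventilatory support windows (28 days in the synopsis follow-up list, 10 days elsewhere) so that the costing has one defined source.

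**Cost.** One more field from an extract already planned, and one line on two forms. The extract can cover patients already enrolled, including those who died or returned no form. This version is dated 26 November 2007, after two of the three recruiting seasons, so the new form line helps only patients still to reach Day 28. Out-of-county stays would rest on self-report. The amendment must go to the ethics committee under section 3.2.

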#### 5 STUDY POPULATION

#### 5.1 Study setting

This study will be done in three hospitals (Leicester Royal Infirmary, Glenfield Hospital, and Leicester General Hospital) that provide acute medical care for the University Hospitals of Leicester (UHL) Trust, Principally in the Medical Assessment Units. The UHL Trust serves a population of approximately 1 million subjects of all ages. The University Hospitals of Leicester NHS Trust is the only facility within the county of Leicestershire providing inpatient emergency medical care to the inhabitants of Leicestershire (population ~ 1 million). The laboratory tests will be carried out in the Molecular Diagnostic Laboratory, and Public Health Laboratory, Leicester Royal Infirmary. The study will carried out during the 36-month period August 1 2005- July 31 2008. Patient enrolment will occur during: September 1 2005 to June 30 2006; September 1 2006 to June 30 2007; & September 1 2007 to June 30 2008.

#### 5.2 Inclusion criteria

Men or women must satisfy the following to qualify for enrolment:

- Able and willing to give written informed consent, OR a relative or carer is able and willing to give informed Assent, OR in the event that Informed Consent or Informed Assent cannot be obtained from the patient or carer (either because: (a) the patient is so sick (breathless or confused) that he/she is temporally unable to assimilate information regarding the study to judge whether to participate; or (b) the patient has pre-senile or senile dementia) f the following are satisfied:
  - (i) The patient provides written informed consent after reading the synopsis of the Patient Information Leaflet (Appendix IVa). In such cases the patient must be asked to provide Informed Consent after perusal of the 'Full' Information Leaflet when he/she is sufficiently well to do so;
- Age ≥65 years, OR age ≥18-64 years with underlying chronic heart or lung disease including asthma, or pneumonia / influenza type symptoms.
- Have an *acute exacerbation* of chronic cardio-pulmonary illness of ≤168 hours (7 days) duration, OR an *acute cardio-pulmonary illness* or influenza-like illness of ≤7 days duration, including:
  - Pneumonia\*,
  - Influenza/influenza-like illness\*,
  - Exacerbations of chronic obstructive pulmonary disease (COPD)\*,
  - Bronchitis\*,
  - Asthma\*,
  - Congestive heart failure\*, Cardiac arrhythmia\*.
- Can be recruited to the study within a 16-hour period of initial assessment by an on-call doctor on the Medical Admissions Unit, or another ward accepting acute medical admissions,
- Able and willing to adhere to the procedures stated in the protocol
- Patients should have access to a telephone.

\*NOTE: these are provisional or suspected clinical diagnoses that have been made either by the referring general medical practitioner or by the admitting medical team in the differential diagnosis. In general, it is expected that participants will have at least one respiratory symptom and one systemic symptom,  $OR \ge 2$  respiratory symptoms from at least two of the following bullet points, including:

#### Respiratory symptoms:

- Sore throat and/or hoarseness
   Nasal symptoms (stuffiness, and/or runny nose, and/or thick nasal discharge, or sneezing)
- Cough (new or increased)
- Sputum (new or increased)
- Wheezing (new or increased)
- Difficulty breathing/shortness of breath (new or increased)
- Chest pain with breathing

#### Systemic symptoms:

- Feverishness/sweating
- Chills, shivers, or rigors
   Tiredness or fatigue
- Decrease or loss of appetite
- Decrease of loss of ag
   Headache
- Muscle or body aches
- Generally feel unwell

